9.4.2.1. Guidance for Cardiac Monitoring Following Treatment Initiation or Re-Initiation

Prerandomization (ie, pre-dose/baseline) vital signs (resting heart rate, systolic and diastolic BP, body temperature, and respiratory rate) will be used as the Baseline measurement. The pre-dose heart rate measurement will be used for comparison to the post-dose measurement. Subjects should receive the first dose of study treatment before 12:00 PM (noon).

First Dose Cardiac Monitoring

In-clinic cardiac monitoring, of at least 4 hours, will occur on Day 1 and will include the following ([Table 3](#)):

- Full baseline vital signs (heart rate, systolic and diastolic BP, body temperature, and respiratory rate) and a 12-lead ECG (taken with the subject in the supine position) will be assessed prerandomization.
- After the first dose of study treatment on Day 1, subjects must remain under observation in the clinic for at least 4 hours.
- At Hours 1, 2, and 3 (\pm 15 minutes) post-dose, the heart rate and systolic and diastolic BP will be assessed with the subject in the sitting position, with the time recorded. If the subject has a heart rate $<$ 50 bpm or if cardiovascular symptoms develop, then the subject should remain closely monitored, including 12-lead ECGs as clinically indicated, until the Hour 4 discharge assessment.
- At the Hour 4 (\pm 15 minutes) discharge assessment, heart rate and systolic and diastolic BP will be assessed with the subject in the sitting position and a 12-lead ECG (with the subject in the supine position) will be performed. Subjects may be discharged from the clinic after the 4-hour assessment if they meet the criteria

described in [Table 4](#). Subjects not meeting the discharge criteria will require extended monitoring as described below.

- Subjects experiencing a clinically relevant treatment-related symptomatic event (eg, chest pain, dizziness, palpitations, or syncope) associated with reduction of the heart rate or clinically relevant 12-lead ECG changes at any time during the 4-hour monitoring period must be discontinued from treatment ([Table 5](#)).

Table 3: Procedures to be Performed During the Monitoring Period

| Procedure | Pre-Dose | Hours 1, 2, 3 Post-Dose ^a | Hour 4 Post-Dose ^a |
|--------------------------------------------|----------|--------------------------------------|-------------------------------|
| Blood pressure and heart rate ^b | x | x | x |
| 12-lead ECG | x | | x |
| Assess discharge criteria | | | x |

^a Measurements may be taken \pm 15 minutes of the scheduled time.

^b Heart rate is based on vital signs.

Table 4: Discharge Criteria After Cardiac Monitoring

| |
|--------------------------------------------------------------------------------------------------------------------------------------------------------------------------|
| Subjects will be released from the clinical site after dosing on Day 1 (but no sooner than 4 hours post-dose) when they fulfill the following discharge criteria: |
| 
 • Heart rate \geq 50 bpm or no more than 10 bpm lower than the pre-dose (baseline) value |
| 
 • No evidence of second-degree AV block or higher |
| 
 • No cardiac symptoms (eg, chest pain, dizziness, palpitations, lightheadedness, shortness of breath, or syncope) |

AV, atrioventricular

Note: Subjects should have written instructions on when to return to the clinic and a 24-hour contact phone number to call in the event of any new or worsened cardiovascular symptoms.

Extended Cardiac Monitoring

Subjects who do not meet discharge criteria at 4-hours post-dose will require extended cardiac monitoring:

- Vital signs will be assessed hourly and 12-lead ECG may be performed, as clinically indicated, until the subject meets the discharge criteria ([Table 4](#)).
- The Medical Monitor should be contacted if the subject does not meet the discharge criteria after \geq 4 hours of extended cardiac monitoring.
- Any subject who requires extended monitoring on Day 1 must return on Day 2 for the second dose and will be re-monitored as on Day 1. These subjects will be discontinued from study treatment if they do not meet the discharge criteria at 4 hours after the second dose. Extended cardiac monitoring should be continued until the subject meets the discharge criteria ([Table 4](#)).
- Subjects experiencing a symptomatic event (eg, chest pain, dizziness, palpitations, lightheadedness, shortness of breath, or syncope) at any time during the 4-hour monitoring period that is not associated with either a reduction in heart rate or clinically relevant change in 12-lead ECG, may be discharged provided they meet the

discharge criteria (Table 4), and as deemed appropriate by the Investigator; however, these subjects must return on Day 2 for the second dose and will be re-monitored as on Day 1. These subjects must be discontinued from treatment if they do not meet the discharge criteria at 4 hours after the second dose on Day 2 and extended cardiac monitoring should be continued until the subject meets the discharge criteria (Table 4).

Study Treatment Discontinuation Related to Post-dose Cardiac Monitoring

A complete list of reasons for study treatment discontinuation is provided in Section 5.1. Reasons for study treatment discontinuation specific to post-dose cardiac monitoring are provided in Table 5. The Medical Monitor should be contacted before discontinuing a subject.

Table 5: Discontinuation of Study Treatment-Related to Post-dose Cardiac Monitoring

| Reasons for Study Treatment Discontinuation Related to Post-Dose Cardiac Monitoring ^a |
|--------------------------------------------------------------------------------------------------------------------------------------------------------------------------------------------------------------------------------------------------------------------------------------------------------------------------------------------------------------------------------------------------------------|
| 
Subjects who have a cardiovascular treatment-related symptomatic event (eg, chest pain, dizziness, palpitations, lightheadedness, shortness of breath, or syncope) associated with reduction of the heart rate or associated with clinically relevant 12-lead ECG changes at any time during the 4-hour monitoring period on Day 1 or Day 2 (as applicable). |
| 
Subjects who have not met the discharge criteria on Day 1 after ≥ 4 hours of extended monitoring, or Day 2 by 4 hours post-dose. |

^a All treatment discontinuations should be discussed with the Medical Monitor.

Cardiac Monitoring Upon Treatment Re-Initiation Following Dose Interruption

Subjects should undergo the same first dose cardiac monitoring procedures as the original treatment initiation when study treatment dosing is interrupted for:

- ≥ 2 consecutive days within the first week of treatment
- ≥ 7 consecutive days after the first week of treatment

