5. REMOVAL OF SUBJECTS FROM STUDY TREATMENT OR ASSESSMENT

5.1. Discontinuation from Study Treatment

A subject's double-blind treatment may be discontinued for any of the following reasons:

- Worsening of disease (Note: If a subject discontinues double-blind treatment at any time starting with the Week 12 assessment, the subject may be eligible to enter the APD334-303 OLE [Section 5.1.1])
- Adverse event that in the judgement of the Investigator and/or Medical Monitor the subject should not continue study treatment
- Subject noncompliance with the protocol or study treatment that is considered significant by the Medical Monitor
- Investigator decision
- Withdrawal by subject or parent/guardian
- Lack of efficacy
- Lost to follow-up
- Study termination by Sponsor
- Other, non-adverse event

A subject's double-blind treatment must be discontinued for any of the following reasons:

- Decline in PFT values (FEV₁ and/or FVC) below 50% of the predicted values
- Confirmed diagnosis of clinically significant macular edema
- Confirmed diagnosis of active TB
- Subjects who have a cardiovascular treatment-related symptomatic event (eg, chest pain, dizziness, palpitations, lightheadedness, shortness of breath, or syncope) associated with reduction of the heart rate or associated with clinically relevant ECG changes at any time during the 4-hour monitoring period on Day 1 or Day 2 (as applicable) (Section 9.4.2.1)
- Subjects who have not met the discharge criteria on Day 1 after ≥ 4 hours of extended monitoring, or Day 2 by 4 hours post-dose (Table 4).
- Pregnancy (Section 9.10.9)
- Suspected drug induced liver injury as defined by the 2009 FDA Guidance for Industry (FDA 2009)
 - ALT or AST $> 8 \times$ ULN
 - ALT or AST $> 5 \times$ ULN for > 2 weeks
 - ALT or AST $> 3 \times$ ULN and (total bilirubin $> 2 \times$ ULN or international normalized ratio > 1.5)
 - ALT or AST $> 3 \times$ ULN with the appearance of fatigue, nausea, vomiting, right upper quadrant pain or tenderness, fever, rash, and/or eosinophilia ($> 5\%$)

Because transient fluctuations of ALT or AST are common, and progression to severe drug-induced liver injury or acute liver failure is uncommon, automatic discontinuation of study treatment upon finding a greater than $3 \times$ ULN elevation of ALT or AST may be unnecessary.

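### The protocol gives two conflicting mandatory instructions (stop treatment, or return for a second dose) for a subject still failing the Day 1 cardiac discharge criteria after 4 or more hours of extended monitoring

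*Protocol*

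**What the plan says.** Section 5.1 of the protocol contains a list introduced by the statement that "double-blind treatment must be discontinued for any of the following reasons". One entry reads "Subjects who have not met the discharge criteria on Day 1 after ≥ 4 hours of extended monitoring"; the same entry has a second branch for subjects who fail on Day 2 by 4 hours after dosing. Table 5, in Section 9.4.2.1, repeats both branches.

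The part of Section 9.4.2.1 on extended cardiac monitoring applies to subjects who fail the Table 4 discharge criteria 4 hours after the first dose. It has hourly vital signs continue until the criteria are met. It then says "The Medical Monitor should be contacted if the subject does not meet the discharge criteria after" 4 or more hours of extended monitoring. The next bullet says "Any subject who requires extended monitoring on Day 1 must return on Day 2 for the second dose", with repeat monitoring, and continues: "These subjects will be discontinued from study treatment if they do not meet the discharge criteria at 4 hours after the second dose".

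A separate stop rule covers treatment-related symptomatic events accompanied by a fall in heart rate or relevant ECG changes. The first-dose monitoring bullets apply it to events occurring "at any time during the 4-hour monitoring period must be discontinued from treatment". Section 5.1 and Table 5 use the same 4-hour window and name Day 1 and Day 2.

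**The concern.** The return rule covers every subject who needs extended monitoring. The Day 1 stop rule covers those among them who are still failing late in the day. The second group lies wholly inside the first, both rules are worded as obligations, and neither refers to the other. Section 9.1 also rules out protocol waivers and exemptions, so a site cannot comply with both.

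The subjects concerned are those with the most persistent first-dose cardiac findings, and Section 1.3 lists first-dose bradycardia and AV block among the events reported for this drug class. The choice of rule decides whether such a subject takes a second tablet.

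It also changes the data. A subject stopped on Day 1 has had one dose and so stays in the Full Analysis Set, ordinarily has no Week 12 or Week 52 assessment, and counts as a nonresponder. A subject who is dosed again may contribute observed outcomes. Disposition counts (SAP Section 10) and the between-arm comparison of adverse events leading to discontinuation (SAP Section 18.1.6) would depend on which passage was followed.

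**Working it through.** No sample size, power or alpha figure is involved, and the plan states no figure to reproduce. The check is a timeline followed by a comparison of the rules.

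**Timeline.** Extended monitoring begins after a failed check at Hour 4. The Day 1 stop needs at least 4 hours of it. Hour 4 + 4 hours = Hour 8 after dosing, or later.

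**Rules side by side, Day 1, for a subject without a symptomatic event:**

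| Course on Day 1 | Section 5.1 and Table 5 | Extended-monitoring bullets, Section 9.4.2.1 |
|---|---|---|
| Meets Table 4 at Hour 4 | No stop | Not applicable |
| Fails at Hour 4, meets Table 4 before Hour 8 | No stop | Second dose on Day 2 |
| Fails at Hour 4, still failing at Hour 8 and at the last Day 1 check | Discontinue | Second dose on Day 2 |
| Fails at Hour 4 and Hour 8, meets Table 4 at Hour 9 | Depends on when the check is made | Second dose on Day 2 |

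The first two rows agree. The third is a direct conflict. The fourth is unclear for another reason: a minimum of 4 hours fixes no single time at which failure is judged.

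**Illustration (invented heart rates).** Table 4 accepts a heart rate of at least 50 bpm, or one no more than 10 bpm below the pre-dose value. Take a pre-dose rate of 62.
- Hour 4, rate 44: below 50, and 62 − 44 = 18 bpm lower. Fails, so extended monitoring starts.
- Hour 8, rate 46: below 50, and 62 − 46 = 16 bpm lower. Fails after 4 hours of extended monitoring.

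If the rate stays there, Section 5.1 and Table 5 discontinue this subject and the return rule brings the subject back for dose 2. If the rate is 53 at Hour 9, the subject is in the fourth row.

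**Symptomatic-event window.** Section 5.1, the first-dose bullets and Table 5 all confine this stop to the 4-hour monitoring period. A qualifying event at Hour 3 is a mandatory stop. The same event at Hour 6, in a subject already held for a failed Hour 4 check, is outside the window as written. If that subject meets Table 4 at Hour 7, the Day 1 discharge stop is not reached either. The three places agree with each other, so this is a limit on coverage and not a contradiction.

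**The case against.** The strongest reply is that the passages can be read together. The stop rule has a Day 1 branch and a Day 2 branch. If every subject with extended monitoring had to be dosed again, the Day 1 branch would have nothing to act on. Reading the return rule as covering only subjects who recover during extended monitoring gives every sentence a purpose. Section 9.4.2.1 also points to Section 5.1 for the complete list of discontinuation reasons. This may well be what was intended. But the return rule says *any* and *must*, with no limit by duration or result, and it puts its own stop after the second dose. A site has to infer the exception.

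A reader might also take the instruction to contact the Medical Monitor as a third, competing outcome. It is not. The text before Table 5 asks for that contact before any discontinuation, and the table's footnote says all discontinuations should be discussed with the Medical Monitor. That routing should reduce differences between sites, although no passage says which rule the Medical Monitor is to apply.

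A reader might infer from the Hour 4 limit that a subject with syncope and a low heart rate at Hour 6 has no protection and has to be dosed again. The documents do not support that. Symptoms block discharge under Table 4. Section 5.1 allows a stop for an adverse event on the judgement of the Investigator or Medical Monitor. Section 9.1 requires immediate safety concerns to go to the Medical Monitor to decide on continuation. What is missing is a mandatory rule for that period.

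Nor is it right that no stop rule reaches re-initiation. Section 9.4.2.1 carries the first-dose procedures over to re-initiation, and the symptomatic-event bullet among them names no day. Only the Section 5.1 and Table 5 versions name Day 1 and Day 2.

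**Conclusion.** The conflict stands for one defined group: subjects who have not met the discharge criteria on Day 1 at about Hour 8 or later. It lies between Section 5.1 and Section 9.4.2.1, and also within Section 9.4.2.1, because Table 5 sits there. It rests on the current wording alone.

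Its size cannot be derived. Someone might assume that 1% to 5% of the 280 etrasimod subjects need extended monitoring, which gives 280 × 0.01 = 2.8 to 280 × 0.05 = 14, or about 3 to 14. That rate is not in the documents, and it counts everyone who fails at Hour 4. The affected group is the subset still failing at Hour 8 or later, which could be empty. An effect on the primary result is not shown and is probably small. The reason to act is that a literal reading of one mandatory rule breaks another at the point of giving a second dose.

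The symptomatic-event window and the wording for re-initiation are secondary coverage gaps. No view is taken here on which clinical rule is right.

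**What to change.** Reconcile Section 5.1, Table 5 and the extended-monitoring bullets of Section 9.4.2.1:

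- Give a subject who has not met Table 4 on Day 1 after 4 or more hours of extended monitoring one stated outcome, in identical words in all three places, and state when that check is made.
- Restrict the return rule to the group it is meant for.
- As a secondary clarification, state whether the symptomatic-event stop runs through extended monitoring, and whether the Table 5 rules that name Day 1 and Day 2 also apply at re-initiation.

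The sponsor decides which outcome applies in each case. The cost is a few sentences in an amendment or site communication, with no new visit or procedure.

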9.4.3. Enrollment in Open-Label Extension Study APD334-303

At the Week 12 assessment a determination will be made regarding continuation into the 40-Week Treatment Period or eligibility for entry into the OLE (Section 5.1.1).

Subjects who discontinue treatment prematurely should have an ET visit as indicated in the Schedules of Assessments (Table 7 and Table 8). If the ET visit is within 4 weeks of the last proctosigmoidoscopy and biopsy, these procedures do not need to be repeated.

9.5. Follow-Up Period

For subjects not participating in the OLE study, a follow-up visit, will be performed at 2 and 4 weeks after the last administration of study treatment as indicated in the Schedules of Assessments (Table 7 and Table 8).

If the ET or Study Completion visit is ≥ 2 weeks after the last administration of study treatment, the 2-Week Follow-Up visit is not required; however, the 4-Week Follow-Up visit should be

scheduled and completed. If the ET or Study Completion visit is ≥ 4 weeks after the last administration of study treatment, the 4-Week Follow-Up visit is not required.

If the absolute peripheral lymphocyte count is not within normal limits at the 4-Week Follow-Up visit, subjects should return for CBC with differential according to local standard of care (captured as subsequent Follow-Up visit or unscheduled visit).

All adverse events should be recorded for 30 days after last administration of study treatment (Section 9.10.8.2.2).

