Subjects who discontinue treatment prematurely, regardless of the reason, should be instructed to return for an Early Termination (ET) visit within 7 days of the last administration of study treatment (Table 7 and Table 8) and before initiation of any new treatments to complete all of the ET assessments. If a subject discontinues due to pregnancy, they are not required to complete the endoscopy. If the ET visit is within 4 weeks of the last sigmoidoscopy and biopsy, these procedures do not need to be repeated.

If the ET visit is ≥ 2 weeks of the last administration of study treatment, the 2-Week Follow-Up visit is not required; however, the 4-Week Follow-Up visit should be scheduled and completed. If the ET visit is ≥ 4 weeks of the last administration of study treatment, the 4-Week Follow-Up visit is not required unless the absolute lymphocyte count (ALC) is not within normal limits.

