9.8.4. Efficacy-Related Biomarkers

Samples for biomarker assessments will be collected according to the Schedules of Assessments (Table 7 and Table 8). Blood, tissue, and stool samples will be analyzed by the central or specialty laboratory. Details for collection, processing, and storage will be provided in the Laboratory Manual. Residual samples will be stored and may be used for additional analyses if the subject has granted consent where allowed by the regulatory authorities and local ethics committees.

C-reactive protein (CRP): CRP is an acute phase protein expressed by hepatocytes in response to inflammatory cytokines and will be assessed using a hs-CRP assay. Investigators will be blinded to the hs-CRP results during the treatment and follow-up periods.

Fecal calprotectin: Fecal calprotectin is a complex consisting of calcium-binding proteins. It is expressed by activated neutrophils (and to a lesser extent by macrophages and monocytes) and fecal levels correlate with the number of neutrophils in the gut. It is used as a biomarker of intestinal inflammation. Investigators will be blinded to the fecal calprotectin results during the treatment and follow-up periods.

Lymphocyte counts: Etrasimod is believed to modulate lymphocyte trafficking resulting in a reduction in peripheral lymphocyte count and lymphocyte availability for recruitment to sites of inflammation. During the treatment period, the Investigator will be blinded to the white blood cell (WBC) and differential counts during the treatment and follow-up periods. During the

treatment period, WBC differential results will be assessed by an unblinded Medical Monitor (not providing direct medical oversight of study conduct). If either of the following occur, the unblinded Medical Monitor will notify the Investigator with additional instructions.

- ANC < 1000 cells/ μ L
- ALC < 200 cells/ μ L

If the ANC is confirmed below the 1000 cells/ μ L limit, the Investigator will be requested to closely monitor for serious infection and institute appropriate follow-up at his or her discretion.

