^a Total WBC, neutrophil, lymphocyte, and TBNK will be available for review prior to randomization. After randomization, the total WBC, neutrophil, lymphocyte, and CD4 T cell counts will be reviewed by an unblinded Medical Monitor who will provide instructions to the site investigator in the event of significant lymphopenia. Investigators will remain blinded to the results after randomization. Refer to Section 9.8.4 for additional details.

^b Investigators will remain blinded to the results after randomization.

^c Stool sample for bacterial culture, ova, and parasite evaluation, and *C. difficile* assay at any point in the study when a subject becomes symptomatic, including worsening or return of disease activity.

β-hCG, human beta-human chorionic gonadotropin; HBsAg, hepatitis B surface antigen; HCV, hepatitis C virus; HIV, human immunodeficiency virus; hs-CRP, high-sensitivity C-reactive protein; IgG, immunoglobulin G; RIBA, recombinant immunoblot assay; TBNK, T lymphocytes, B lymphocytes, and natural killer lymphocytes; WBC, white blood cells

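### Post-treatment recall depends on whether the lymphocyte count is normal, but the protocol gives no route by which a blinded site learns of a below-normal count of 200 cells/µL or more

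*Protocol*

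**What the plan says.** **Rules that depend on the count.** Section 9.5 has the subject return for a complete blood count with differential "If the absolute peripheral lymphocyte count is not within normal limits at the 4-Week Follow-Up visit". Footnote b of Table 7 and footnote b of Table 8 say the same. Section 5.1 deals with an Early Termination visit 4 weeks or more after the last dose: the 4-Week visit is then "not required unless the absolute lymphocyte count (ALC) is not within normal limits". Section 9.5 and both footnotes waive the 4-Week visit in that situation without the lymphocyte exception.

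**Rules on who sees the count.** Section 9.8.4 states that "the Investigator will be blinded to the white blood cell (WBC) and differential counts during the treatment and follow-up periods". Footnote a of Table 6 says "Investigators will remain blinded to the results after randomization. Refer to Section 9.8.4 for additional details". Section 9.10.7 takes total white cells and lymphocytes out of the Investigator's ordinary laboratory review and points to Section 9.8.4.

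**Rules on who tells the site.** Under Section 9.8.4, in the "treatment period, WBC differential results will be assessed by an unblinded Medical Monitor" who does not provide direct medical oversight. Then: "If either of the following occur, the unblinded Medical Monitor will notify the Investigator with additional instructions". Two events are listed: a neutrophil count below 1000 cells/µL, and "ALC < 200 cells"/µL. Blinded values may be released only once there has been at least one lymphocyte count below 200.

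**The concern.** Etrasimod is expected to lower circulating lymphocytes (Section 1.3). The recall rule is the protocol's check that they recover after treatment stops. It applies to subjects who do not enter the open-label extension, since only they have follow-up visits. If nobody passes on a below-normal result, a subject whose count has not recovered can leave the study without the repeat counts the protocol asks for, and no one will have departed from the text. The late Early Termination case adds a second problem: Section 5.1 and Section 9.5 give different answers on whether the 4-Week visit is needed at all.

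**Working it through.** The plan gives no figure to reproduce and no arithmetic applies beyond a unit conversion. The check is to follow one follow-up result through the text.

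1. **Is there a result?** Yes. Tables 7 and 8 schedule a blood count with differential at both follow-up visits, and Section 9.1 has protocol-required tests done centrally unless otherwise stated.
2. **Can the Investigator see it?** No. Section 9.8.4 names the follow-up period in the blind. Its sentence is muddled, because it opens by referring to the treatment period alone, but footnote a of Table 6 starts the blind at randomization and gives no end.
3. **Does anyone else see it?** Section 9.8.4 describes the Medical Monitor's review for the treatment period. Footnote a places the review after randomization and can be read as reaching into follow-up.
4. **Is that person told to contact the site?** This depends on the value:

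| Follow-up lymphocyte count | Return required by 9.5? | Stated route to the site |
|---|---|---|
| Within normal limits | No | None needed |
| Below normal, 200 cells/µL or more | Yes | None |
| Below 200 cells/µL | Yes | Monitor notifies, if the review extends to follow-up |
| Above the upper limit | Yes, on the literal wording | None |

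The second row is the gap that matters. Its lower edge is 200 cells/µL. Its upper edge is the laboratory's lower limit of normal, which the documents do not give. The entry minimum in Inclusion Criterion 9 is 0.8 × 10⁹/L; dividing by 10⁶ µL per litre gives 800 cells/µL. That is an eligibility threshold and cannot stand in for the normal limit.

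5. **Does another provision cover the second row?** Footnote a has the monitor instruct the site in the event of significant lymphopenia, but it sets no threshold and refers back to Section 9.8.4, where the lymphocyte figure is 200. The weekly repeats until the count exceeds 500 also start from a count below 200.
6. **Late Early Termination visit.** Under Section 9.5 the 4-Week visit is waived, and the recall condition attached to that visit goes with it. Under Section 5.1 the visit is kept if the count is abnormal, but the site again lacks the count. The two provisions conflict whatever the blinding rule.

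**The case against.** The strongest reply is that neither Section 9.5 nor Section 5.1 says the Investigator must judge normality. Footnote a already describes someone who sees the counts after randomization and has a channel to the site, so the rules are compatible with the monitor making that judgement. A laboratory manual or monitoring plan might also contain the alert. This stands in part: a person and a channel exist. What is missing is any instruction to use the channel for a count that is below normal but not below 200, and neither Section 9.5 nor Section 9.8.4 points to another document for this purpose.

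The reply also limits how far the point can go. Three stronger readings are tempting:

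- **That the rule cannot be carried out at all.** A reader might infer this from the blind. The documents do not support it: counts below 200 have a stated route if the monitor's review continues into follow-up, and footnote a allows that reading.
- **That most incomplete recoveries fall in the gap.** No figure in the documents supports this. The only recovery statement, in Section 1.3, is that counts were within normal limits by 7 days after the last dose, which is 28 − 7 = 21 days before the 4-Week visit.
- **That the SAP's lymphocyte recovery table would lose values.** SAP Section 18.3.1 tabulates lymphocyte recovery at the 2-Week, 4-Week and last follow-up. The repeat counts follow local standard of care, and SAP Section 18.3 excludes local results from summaries except lipid and thyroid panels. If the repeats are local, they would not enter the table even with perfect notification. Only if they go to the central laboratory would missed recalls thin the last-follow-up row, and the 2-Week and 4-Week rows would be unaffected.

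A recall notice also has a cost: lymphopenia is the drug's expected effect, so the notice may hint at assignment.

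**Conclusion.** The inconsistency holds. For a follow-up lymphocyte count from 200 cells/µL up to the lower limit of normal, the protocol requires a return visit, withholds the result from the Investigator, and tells no one to pass it on. Followed literally, the rule would not be triggered for these subjects. This is a failure of a stated safety rule and should be corrected.

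The number affected cannot be derived from the documents and may be small, given Section 1.3. The conclusion assumes that the blind runs through follow-up, as Section 9.8.4 states, and that no alert for this purpose exists outside the protocol. It concerns safety follow-up and blinding; the primary and key secondary efficacy analyses are not touched.

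**What to change.** Reconcile Sections 5.1, 9.5 and 9.8.4, footnote a of Table 6, and footnote b of Tables 7 and 8, so that together they state:

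- whether the blind to lymphocyte counts applies in follow-up, including to a repeat count done locally, which could show the site the value;
- who sees the follow-up count and compares it with the normal limits;
- how the site learns that a return visit is due, for example by a notice that does not carry the value.

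Also reconcile Section 5.1's lymphocyte exception to waiving the 4-Week visit with Section 9.5 and the two footnotes, which omit it. If an alert already exists in another study document, a cross-reference to it would answer the notification question.

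The cost is protocol wording and a notification route, with no new scheduled sample. The remaining downside is the hint at assignment, which arises only after the subject's double-blind treatment has ended.
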